6.1.1 Induction Therapy: Week 0 to Week 12 (Last Dose at Week 10)

Double-blind Induction Therapy is separated into Part A for administration of multiple ascending IV doses of KHK4083 (or placebo) to subjects in Cohorts 1 - 3 and Part B for administration of the recommended IV dose (one of three dose levels identified in Part A) of KHK4083 (or placebo) to subjects in Cohort 4. Subjects in Part A are prohibited from participating in Part B.

Subjects in each cohort will be randomly assigned in a 3:1 ratio to receive KHK4083 or placebo by IV infusion over 60 minutes (\pm 10 minutes). Each subject will receive a total of 6 treatments (one IV infusion per treatment) every 2 weeks from Week 0 (Day 1) to Week 10 of Induction Therapy. Safety assessments (e.g., after 2 treatments for 1.0 mg/kg and 3 treatments for 3.0 and 10 mg/kg are administered and 14-day safety data from the last treatment are available) will determine whether dosing will continue for subjects within a cohort and if the investigational product will be administered at the next higher dose level for subjects in the next cohort in Part A or for Cohort 4 in Part B (refer to Section 6.3 for details on the Safety Monitoring Plan).

For subjects in all cohorts, a sigmoidoscopy with biopsy is scheduled at Week 12 to assess improvement in the mucosa from Baseline (Week 0) to Week 12. It is highly recommended that the sigmoidoscopy with biopsy be performed within 7 to 13 days prior to the Week 12 visit. The sigmoidoscopy results from the central reader are required before a subject receives treatment in the OLE/LTE Therapy phase.

6.1.2 Long-term Extension Therapy: Week 12 (First Dose) to Week 52

The LTE is only active for subjects who entered it prior to approval of Amendment 2. Subjects who sign an ICF under Amendment 2 are eligible for the OLE (see Section 6.1.3).

Subjects who completed double-blind Induction Therapy (i.e., at least five of six treatments) and had a clinical response or mucosal healing were eligible to continue in double-blind LTE Therapy. A clinical response is defined as a reduction in the total Mayo Clinic score of at least 3 points and a decrease of at least 30% from Baseline (Week 0) to Week 12, and a reduction in the rectal bleeding subscale of at least 1 point from Baseline (Week 0) to Week 12 or an absolute rectal bleeding score of 0 or 1 at Week 12. Mucosal healing is defined as a mMES of 0 or 1.

All subjects who qualified were to have been given two options:

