6.1.4 Transitioning from the Long-term Extension to the Open-label Extension

Subjects participating in the double-blind LTE who experience a clinical worsening or a flare of disease up to Week 28, as defined by the Investigator, may transition to the OLE. Subjects will maintain the same visit schedule, e.g., a subject who completed a Week 20 visit in the LTE and transitions to the OLE at Week 24 will have an OLE Week 24 visit. However, for the first two open-label doses in the OLE, additional safety monitoring will include ECGs and post-infusion monitoring as performed for the OLE Week 12 and Week 16 visits, respectively.

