8.5 Prior and Concurrent Therapy

All medications (including prescription, non-prescription and supplements) for treatment of UC taken within 6 months prior to Screening; any other medication taken 1 month prior to Screening; and any concomitant medications (including tracking probiotic usage) during the study will be collected. For all biologic treatments, the reason for discontinuation should be collected at Screening. Combination medications should be recorded by trade name.

Stable doses of the following concomitant medications are permitted for UC treatment during the study as specified below:

- Aminosalicylates (5-ASA or mesalamine ≤ 4.8 g/day; sulfasalazine ≤ 3 g/day) for at least 14 days prior to the Screening visit; and/or
- Oral glucocorticoids, ≤ 20 mg/day prednisolone or the equivalent, or budesonide ≤ 9 mg/d for at least 14 days prior to the Screening visit (or for 4 weeks if a course of corticosteroids had started at less than 8 weeks prior to Screening visit); and/or
- Azathioprine up to 3 mg/kg/day or 6-mercaptopurine up to 1.5 mg/kg/day for a total treatment period of at least 12 weeks, including 4 weeks of stable treatment, prior to the Screening visit.

Supportive therapy to manage symptoms or AEs is acceptable. Daily, chronic antidiarrheals should not be taken.

One bolus or “rescue” treatment for up to 7 days with each of the following: systemic corticosteroids or topical corticosteroid enemas or suppositories (in addition to the dose of oral corticosteroids at Screening) is permitted only after Week 12 evaluations are complete. Topical anti-inflammatory agents may be permitted only after Week 12 evaluations are complete and application must be withheld for at least 2 weeks prior to the sigmoidoscopy at Week 52/End-of-Treatment visit.

Dose reductions of concurrent medications are permitted for AEs from Baseline through the end of the study as allowed by the protocol. Other dose adjustments of concurrent medications (including corticosteroids and other treatments for UC) are permitted after the Week 12 visit (per Investigator’s judgment), i.e., during OLE/LTE Therapy and the Induction Therapy and OLE/LTE Therapy Follow-up Periods. After the Week 12 visit, corticosteroid (glucocorticoid) dosages of prednisolone or its equivalent may be tapered by approximately 2.5 mg/day per week, at the Investigator’s discretion. Subjects who have recurrence of clinical symptoms may increase their chronic (> 7 days) dose of corticosteroids and other

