10.3 Exploratory Endpoints

Efficacy and PD exploratory endpoints will be included in this study for all subjects with moderately active UC who receive both Induction Therapy and OLE/LTE Maintenance Therapy. The exploratory endpoints for all subjects who receive both Induction Therapy and OLE/LTE Maintenance Therapy are as follows:

- Clinical improvement at Week 52;
Improvement will be based on a reduction (mean change from Baseline [Week 0] to Week 52) in the total Mayo Clinic score (0 to 12).
- Clinical improvement at Weeks 16, 20, 24, 28, 32, 36, 40, 44, 48, and 52 and at OLE/LTE Therapy Follow-up Period visits (Weeks 56, 60, and 64);
Improvement will be based on mean changes from Baseline (Week 0) in the partial (excludes endoscopy subscores) Mayo Clinic score (0 to 10).

- Clinical response at Week 52;
A clinical response is defined as a reduction in the total Mayo Clinic score of at least 3 points and a decrease of at least 30% from Baseline (Week 0) to Week 52, and a reduction in the rectal bleeding subscale of at least 1 point from Baseline (Week 0) to Week 52 or an absolute rectal bleeding score of 0 or 1 at Week 52.
- Clinical remission (i.e., a total Mayo Clinic score of ≤ 2 and no subscores > 1) at Week 52;
- Durable clinical responses and durable clinical remissions at Week 52 (i.e., present at both Week 12 and Week 52), and glucocorticoid-free clinical remission at Week 52;
- Mucosal healing (i.e., an mMES of 0 or 1) at Week 52;
- Improvement in the mucosa according to the following assessments:
 - At least a 1-point improvement in the mMES from Baseline (Week 0) to Week 52;
 - A mean change in the UCEIS score from Baseline (Week 0) to Week 52; and/or
 - At least a 1-point improvement in the modified Baron endoscopic score from Baseline (Week 0) to Week 52.
- Remission (i.e., mMES of 0 or 1, stool frequency subscore of 0 or 1, and rectal bleeding subscore of 0) rates at Week 12 and Week 52;
- Improvement in the HRQL, which will be based on the subject's completed IBDQs;
- Lowered corticosteroid (glucocorticoid) dosages;
- Glucocorticoid-free treatment duration from Week 16 through Week 52, and through the OLE/LTE Therapy Follow-up Period (Week 56 through Week 64);
- PD profile of KHK4083;
- PK-PD relationships.

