7.3 Analysis of exploratory efficacy endpoints

All exploratory efficacy variables will be summarized by treatments. The changes from Baseline in mMES, UCEIS and total Mayo Clinic score as well as Baseline and Week 52 will be summarized by treatments. In addition, the partial Mayo Clinic scores (without sigmoidoscopy) and changes from Baseline will be summarized by study visit at Weeks 16, 20, 24, 28, 32, 36, 40, 44, 48, and 52 and at OLE/LTE Therapy Follow-up Period visits (Weeks 56, 60, and 64).

The change from Baseline in HRQL based on IBDQ will be analyzed for total score and 4 subscale scores at all study visits (Weeks 2 to 52, including Induction Therapy Follow-up Period visits (Weeks 16, 20, and 26) and OLE/LTE Therapy Follow-up Period visits (Weeks 56, 60, and 64).

Remission (mMES of 0 or 1, stool frequency subscore of 0 or 1 and rectal bleeding subscore of 0) rates at Week 12 will be summarized. Remission rates at Week 52 will be summarized by Double-Blind Period and OLE Therapy Period as well.

Clinical response and clinical remission will be summarized at Week 52. The percentage of subjects with mucosal healing, and the percentages of subjects with improvement in the mucosa (change from Baseline of at least a 1-point improvement in the mMES and/or in the modified Baron endoscopic scores) at Week 52 will be summarized by Double-Blind Period and OLE Therapy Period.

Durable clinical response and durable clinical remission at Week 52 will be summarized by Double-Blind Period and OLE Therapy Period. Durable clinical response and durable clinical remission at Week 52 will be defined as follows:

- Duration clinical response at Week 52 will be defined in the case that clinical response is present at both Weeks 12 and 52.
- Duration clinical remission at Week 52 will be defined in the case that clinical remission is present at both Weeks 12 and 52.

Glucocorticoid-free clinical remission at Week 52 will be summarized by Double-Blind Period and OLE Therapy Period. At Weeks 16 through 52 and through the OLE/LTE Therapy Follow-up Period (Week 56 through Week 64), the change from baseline in corticosteroid (glucocorticoid) dosages and the duration of glucocorticoid-free treatment will be summarized. Those parameters definitions are shown below.

- Glucocorticoid-free clinical remission at Week 52

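### The durable response definition ignores the interval between Weeks 12 and 52, so Week 12 responders who flared in the LTE and switched to open-label KHK4083 can count as durable in the OLE summary

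*SAP*

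**What the plan says.** **Definition.** Protocol 10.3 lists "Durable clinical responses and durable clinical remissions at Week 52 (i.e., present at both Week 12 and Week 52" among the exploratory endpoints. SAP 7.3 carries this over for response ("Duration clinical response at Week 52 will be defined in the case that clinical response is present at both Weeks 12 and 52") and for remission ("Duration clinical remission at Week 52 will be defined in the case that clinical remission is present at both Weeks 12 and 52"). Neither document sets a condition on what happens between the two visits.

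**Reporting.** SAP 7.3 states: "Durable clinical response and durable clinical remission at Week 52 will be summarized by Double-Blind Period and OLE Therapy Period". SAP 4.1 defines the Double-Blind Therapy Period as Induction plus LTE. SAP 3.4.3 applies the exploratory endpoints to everyone who received Induction and OLE/LTE therapy.

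**Route into the LTE and out of it.** Protocol 6.1.2 says that subjects who completed Induction and "had a clinical response or mucosal healing were eligible to continue in double-blind LTE Therapy". Protocol 6.1.4 then opens transfer to the OLE to one group, "Subjects participating in the double-blind LTE who experience a clinical worsening or a flare of disease up to Week 28". The investigator judges whether this has happened, and the visit schedule of those who transfer does not change.

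**Handling of switchers.** SAP 5.1 counts the subjects who moved from LTE to OLE, but only in the disposition table. SAP 4.4 presents available data at each time point and has no rule for a switch or for rescue. Table 2 of the SAP (footnote 3) keeps placebo-randomised subjects in a Placebo category while they receive KHK4083 in the OLE.

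**The concern.** Durability is a statement about an interval, but the rule looks only at its two ends. Once Amendment 2 let LTE subjects who worsened change treatment, one path through the study became response, flare, open-label drug, response again. A reader would call that recapture of response. The rule calls it durable.

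Protocol 6.2 gives assessment of durable response and durable remission among the reasons for the 40-week extension. In the OLE summary, subjects who flared and were recaptured would be indistinguishable from subjects who went straight into the OLE at Week 12 and responded at both visits without a recorded flare-and-switch. The groups are small, so a few such subjects can change the reported rate noticeably.

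**Working it through.** **1. The plan's own counts.** Part A is 3 × (9 + 3) = 36 and Part B is 18 + 6 = 24, so 36 + 24 = 60 randomised. The dropout figure reproduces: 51/(1 − 0.15) = 60. Placebo is 9 + 6 = 15 and the recommended dose is 9 + 18 = 27. These totals do not decide the point, but they supply plausible denominators for step 4.

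**2. The rule applied to every case.** Under the SAP, durable = response at Week 12 AND response at Week 52. Under the alternative, durable = response at Week 12 AND response at Week 52 AND no LTE-to-OLE transition.

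| Week 12 response | Week 52 response | LTE-to-OLE switch | SAP rule | With switch counted |
|---|---|---|---|---|
| yes | yes | yes | durable | not durable |
| yes | yes | no | durable | durable |
| yes | no | yes or no | not durable | not durable |
| no | yes | yes or no | not durable | not durable |
| no | no | yes or no | not durable | not durable |

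Only the first row changes. The path is open: a Week 12 responder qualifies for the LTE, a flare permits the switch, and the unchanged schedule still brings a Week 52 assessment. An LTE entrant with mucosal healing but no clinical response at Week 12 falls in the last two rows and is not affected for durable response. Remission has the same truth table with its own criterion.

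**3. Where the case is reported.** A switcher's Week 52 visit lies in the OLE, so by SAP 4.1 it belongs to the OLE Therapy Period summary and adds nothing to the Double-Blind numerator. The Double-Blind denominator is less clear. SAP 4.1 bases percentages on subjects with a reported value, while SAP 4.4 uses the number in the treatment or cohort group. With D durable subjects, n in the group and s switchers, the rate is D/(n − s) under the first reading and D/n under the second. At an assumed n = 9 and s = 1 the ratio is 9/8 = 1.125. Under the first reading, leaving out one flared subject raises the rate by an eighth of its value.

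**4. Size.** One reclassified subject moves a group's rate by 100/n points:

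- n = 3: 33.3
- n = 9: 11.1
- n = 15: 6.7
- n = 27: 3.7

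These n are planned randomised counts used as assumptions. The actual LTE and OLE denominators and the number of switchers are not in the documents.

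**5. Can the SAP condition on the interval?** Yes. In the same section, glucocorticoid-free clinical remission requires no listed glucocorticoid from Week 16 through Week 52. The durable endpoints have no comparable condition, although SAP Version 2 (06 Oct 2017) postdates Amendment 2 (04 Oct 2016) and already counts switchers in disposition.

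**The case against.** The SAP implements the protocol's definition faithfully. The endpoint is exploratory, no Type I error control is claimed (Protocol 12.3.5), the LTE is closed to new entrants, and SAP 9.4 lists no table titled durable response. All of that stands. It limits the weight of the point but does not remove it, because SAP 7.3 still commits to the summary.

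Four stronger readings are tempting, and the documents do not support them.

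- **Switchers had documented loss of response, so their true durable rate is zero.** The trigger is an investigator-defined worsening or flare, whereas clinical response is measured on total Mayo score against Baseline. No sigmoidoscopy is scheduled between Weeks 12 and 52, so formal loss of response is not shown. A subject could go from 9 to 2, worsen to 4, and still meet the definition. Zero follows only if the switch itself is counted as failure.
- **The double-blind durability result is inflated by recaptured responders.** The split by period keeps their Week 52 results out of that numerator. Only the denominator is open, as shown above.
- **Placebo responses are credited to KHK4083 dose groups.** Placebo-randomised subjects keep their own OLE column. What that column lacks is a note that treatment changed between the two visits.
- **Rescue treatment undermines the endpoint in the same way.** Protocol 8.5 allows steroid rescue once the Week 12 assessments are done, both systemic and local ("topical corticosteroid enemas or suppositories (in addition to the dose of oral corticosteroids at Screening) is permitted only after Week 12 evaluations"), and the durable rule ignores it. But topical anti-inflammatory agents must be withheld for at least 2 weeks before the Week 52 sigmoidoscopy, and the SAP separately reports glucocorticoid-free remission, dosages and glucocorticoid-free duration. These do not cover every rescue, so a sensitivity summary is reasonable, but not a change of the main rule.

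**Conclusion.** The point holds in a narrow form. By the text of SAP 7.3, an LTE subject who met the criterion at Week 12, switched to open-label KHK4083 for worsening by Week 28 and met it again at Week 52 is counted as durable in the OLE Therapy Period summary, and nothing in either document excludes, reclassifies or separates that subject. The effect per subject is about 11 points at an assumed n of 9 and 33 points at an assumed n of 3. The total effect cannot be stated without the number of switchers.

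Two assumptions carry this. The first is that a move to open-label drug for a flare should not be called durability without qualification. The second is that SAP 4.1 places the switcher's Week 52 result in the OLE period. SAP Figures 3 and 4, which illustrate the summary patterns, were not available for this check. It is a worthwhile, inexpensive correction to an exploratory endpoint.

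**What to change.** In SAP 7.3:

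1. Count an LTE-to-OLE transition for worsening as not durable, for both response and remission. Protocol 6.1.4 allows the move only for worsening or flare, so the recorded transition identifies these subjects.
2. Keep those subjects in the Double-Blind Period denominator as not durable. This also settles the difference between SAP 4.1 and 4.4 for this endpoint.
3. In the OLE summary, show switchers who meet the criterion at both visits in a separate 'recaptured response' row, apart from direct OLE entrants.
4. Footnote the Placebo column of the OLE summary: the Week 12 response was on placebo and the Week 52 response on KHK4083.
5. Keep the protocol's two-visit definition as a supplementary summary. Optionally add a sensitivity summary that counts rescue steroid use between Weeks 12 and 52 as not durable.

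Do not require both responses on the same KHK4083 dose. Read literally, that would fail every placebo LTE subject and would count a cohort-level dose reduction (Protocol 6.3) as loss of durability.

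The cost is SAP wording, a few table rows and slightly lower reported durable rates. The data are already collected, since SAP 5.1 counts the movers. Because the main rule would then differ from Protocol 10.3, the departure should be described in the study report, as Protocol 12.8 requires. No clinical rule changes.
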